4.1. Analyses for the Entire Study

The study design includes a 33-36 months of DB period and an OLE period. The primary objective is to evaluate the efficacy and safety of vutrisiran compared with placebo during the DB period. In addition, the long-term efficacy of vutrisiran will be evaluated during the entire study period and the long-term safety of vutrisiran will be evaluated during the entire vutrisiran treatment period.

Two pivotal trials in ATTR-CM, including ATTR-ACT and ATTRibute-CM, indicated that therapeutics with upstream mechanisms of action (MoAs) take ~18 months to manifest benefit on mortality. **CCI**

The different analysis periods, analysis population, data inclusion strategies and description of treatment arms are summarized in [Table 1](#).

Table 1: Summary of Analysis Periods

Analysis Period	Analysis Population	Data Inclusion	Treatment arm description
During the DB period	FAS, mono-FAS SAF, mono-SAF PD/PK Analysis Set	Including all data during the DB period	Placebo; vutrisiran.
During the DB + 6 months OLE period	FAS, mono-FAS (for analysis of outcome endpoints only)	Including all data during the DB period and within 6 months of the first OLE dose	Placebo; vutrisiran.
During the Study	FAS, mono-FAS	Including data during the entire study, integrating the DB and OLE periods	Placebo; vutrisiran.
During vutrisiran treatment [1]	All Vutrisiran Treated Set Mono All Vutrisiran Treated Set	Including data after the first dose of vutrisiran (taken during DB or OLE)	Placebo/vutrisiran; vutrisiran/vutrisiran; total

[1] For placebo patients crossing over to vutrisiran, baseline tafamidis subgroup will be redefined using the tafamidis use status prior to the first dose of vutrisiran.

4.2. Analysis Cutoff and Database Lock

The study has two planned analyses: the Primary Analysis and the Final Analysis.

The Primary Analysis will be performed after the last patient has completed the period of DB exposure or otherwise discontinued. As the study will be ongoing with patients in the OLE period or safety follow-up period, the study database will be locked with all data up to a prespecified cutoff date quality controlled (approximately when the last patient enrolled into OLE), i.e., data in the electronic data capture system will be cleaned and frozen and external laboratory data will be cleaned and quality controlled (and quality assured, where appropriate). Details regarding the database lock process are documented in the study Data Management Plan.

For the Primary Analysis, data on or prior to the prespecified cutoff date will be included. Survival follow-up data after the cutoff date will be kept in the dataset to determine the survival status of patients at the time of cutoff. For assessments with starting/ending dates (e.g., AEs, medications etc.), the starting date will be compared with the cutoff date.

The Final Analysis will be conducted after the study is completed, i.e., all patients have either discontinued or completed all periods of the study.

4.3. Baseline Definition

Baseline definitions will be defined separately for analyses during the DB Period, the entire study period, and the vutrisiran treatment period.

DB period analyses and entire study period analyses

For efficacy parameters, baseline will be defined as the last non-missing value available on or before the date of the first dose of study drug, unless otherwise specified. For 6-MWT, if a patient walked for ≤ 4 minutes at Day 1 visit, the screening visit will be used as baseline.

For PD parameters (TTR, Vitamin A), baseline will be defined as the average of all records prior to the date and time of first dose.

For laboratory parameters (including cardiac biomarkers) and vital signs, baseline will be defined as the last non-missing value prior to the date and time of the first dose of study drug. Only central laboratory (PP) results will be used, unless otherwise specified. For troponin I, the local laboratory results for site 171 patients will be used as baseline for these patients in absence of pre-dose central laboratory results.

CCI

Vutrisiran treatment period analyses

For patients who received vutrisiran in the DB period, their baseline in the vutrisiran treatment period will be the same as that in the DB period.

For patients who received placebo in the DB period, their baseline in the vutrisiran treatment period will be defined as the last non-missing value prior to the first dose in the OLE period, unless otherwise specified.

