3. INVESTIGATIONAL PLAN

3.1. Summary of Study Design

This is a Phase 3, randomized (1:1), double-blind, placebo-controlled, multicenter study to evaluate the efficacy and safety of vutrisiran in approximately 600 patients with ATTR amyloidosis (hATTR or wtATTR) with cardiomyopathy. Approximately 20% of the study population is anticipated to have hATTR and 80% wtATTR amyloidosis with cardiomyopathy.

At baseline, patients are either:

- Tafamidis-naïve (see inclusion criterion #4 for definition); or
- Currently receiving tafamidis (Note: must be on-label use of commercial tafamidis per an approved cardiomyopathy indication in the country of use).

The study consists of 4 periods (Figure 1):

1. **Screening Period:** Up to 45 days during which patients will undergo screening assessments to determine eligibility.

2. Double-Blind (DB) Period:

- At the start of the DB Period (on Day 1), eligible patients will be randomized in a 1:1 ratio to receive blinded doses of 25 mg of vutrisiran or placebo administered as a SC injection q3M (every 12 weeks ±7 days) for up to 36 months.
 - In addition to study drug, all patients will take the recommended daily allowance of vitamin A during their DB Period and Follow-up Period (see below).
- Patients will undergo assessments as outlined in the Schedule of Assessments (Table 1).
- An individual patient's DB Period visits will end after they complete their Month 36 visit, or 30 months after the last patient is randomized, whichever comes first. As such, a patient's last visit during the DB Period may vary from 30 to 36 months after enrollment.
 - The variable length of the DB Period will mean that some patients will not have a Month 33 and/or Month 36 visit. For patients whose last visit in the DB Period was Month 30 (Week 132), Day 1 in the OLE Period will occur 144 weeks (±7 days) after enrollment in the DB Period. For patients whose last visit in the DB Period was Month 33 (Week 144), Day 1 in the OLE Period will occur 156 weeks (±7 days) after enrollment in the DB Period. For patients whose last visit in the DB Period was Month 36 (Week 156), Day 1 in the OLE Period will occur on the same day (since study drug is not administered as part of the Month 36 DB visit).
 - The period of DB exposure, defined as the duration prior to first exposure to open-label treatment, will be 144 to 156 weeks (33 to 36 months).

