 - iv. If the patient has evidence of a MGUS (Section 6.5.5.1) based on serum and urine protein electrophoresis and serum free light chains, the following is required: documentation of TTR protein in cardiac tissue with immunohistochemistry or mass spectrometry; OR, documentation of TTR protein in noncardiac tissue (eg, fat pad aspirate, salivary gland, median nerve connective sheath) with immunohistochemistry or mass spectrometry AND Grade 2 or 3 cardiac uptake on technetium scintigraphy per item 2biii above.
- 3. Medical history of HF with at least 1 prior hospitalization for HF (not due to arrhythmia or a conduction system disturbance treated with a permanent pacemaker) **OR** clinical evidence of HF (with or without hospitalization) manifested by signs and symptoms of volume overload or elevated intracardiac pressures (eg, elevated jugular venous pressure, shortness of breath or signs of pulmonary congestion on x-ray or auscultation, peripheral edema) that currently requires treatment with a diuretic.
- 4. Patient meets one of the following criteria:
 - a. Tafamidis-naïve and not actively planning to commence treatment with tafamidis during the first 12 months following randomization (per exclusion criterion #7) (Note: in addition to patients who have never taken tafamidis, those who have previously been on tafamidis and have not received any tafamidis for at least 30 days before the Screening Visit will be considered tafamidis-naïve for purposes of this study); or
 - b. On tafamidis (Note: must be on-label use of commercial tafamidis per an approved cardiomyopathy indication and dose in the country of use)
- 5. Patient is clinically stable, with no CV-related hospitalizations within 6 weeks prior to randomization, as assessed by the Investigator.
- 6. Screening ccl ; in patients with permanent or persistent atrial fibrillation, Screening ccl
- 7. Able to complete ≥150 meters on the 6-MWT at Screening.

Informed Consent

9. Patient is able to understand and is willing and able to comply with the study requirements and to provide written informed consent.

10. Patient agrees to sign a separate medical records release form, where allowed by local regulations, to allow for the collection of information on vital status, cardiac transplant procedures, left-ventricular assist device placement, and hospitalizations, for the duration of the DB Period of the study (see Section 6.1).

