6.2.2. Vital Status Check

Vital status checks will be performed at the timepoints specified in the Schedules of Assessments (Table 1 and Table 2). Given that heart transplantation or left-ventricular assist device implantation procedures will be considered deaths for the purposes of the primary analysis, vital status checks should include checking for the occurrence of these procedures.

Also see Section 4.3.2.1 for the collection of vital status after withdrawal of consent and Section 4.3.3 for patients who are lost to follow-up.

6.2.3. 6-Minute Walk Test (6-MWT)

Full details regarding the 6-MWT are provided in the relevant study manual.

The 6-MWT is an assessment of functional exercise capacity. The 6-MWT will be administered by staff trained in the procedure per the relevant study manual. When possible, the staff administering the 6-MWT will be different from the Investigator or designee managing the care of the patient. In all cases these staff must be qualified by the central 6-MWT vendor.

The 6-MWT will be performed at each of the timepoints specified in the Schedule of Assessments (Table 1).

At Screening, the 6-MWT will be administered for study eligibility purposes (per inclusion criterion #7 [Section 4.1]). Before conducting the 6-MWT at Screening, the site staff will familiarize the patient with the purpose and conduct of the 6-MWT, as described in detail in the relevant study manual. Familiarization can be repeated at other timepoints if deemed helpful.

When performed on dosing days, the 6-MWT will be performed prior to study drug administration.

Patients who are hospitalized during the study should wait at least 2 weeks after hospitalization before completing a 6-MWT assessment; less time post-hospitalization may be permitted if, in the opinion of the Investigator, the patient is unencumbered due to the recent hospitalization.

In addition, if a patient is not feeling well due to an external factor (eg, flu, sprained ankle, pulled back muscle) at a visit when the 6-MWT will be performed, the test should not be done and should be rescheduled for another day, if possible within the permitted visit window (±7 days).

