5.7.4. Evaluation of Subgroups

All analysis and summary results are presented by baseline tafamidis use subgroups, with vutrisiran monotherapy subgroup defined as an analysis population and background tafamidis defined as a key subgroup. Additionally, subgroup analyses will be conducted to assess the consistency of treatment effect within various subgroups defined by baseline characteristics as listed in the following table.

Subgroup	Overall population	Vutrisiran Monotherapy subgroup
Baseline tafamidis use (yes; no)	Yes	N/A
Age group (<75; ≥75)	Yes	Yes
ATTR disease type (hATTR; wtATTR)	Yes	Yes
NYHA class (I/II; III)	Yes	Yes
Baseline NT-proBNP (≤2000; >2000 ng/L)	Yes	Yes

Subgroup analyses will be performed for the composite endpoint of all-cause mortality and recurrent CV events, 6-MWT, KCCQ-OS, all-cause mortality, NYHA class, and recurrent CV events in both the overall population and vutrisiran monotherapy subgroup. The analyses will be conducted based on the subgroup data only.

- Composite endpoint of all-cause mortality and recurrent CV events:

Composite endpoint of all-cause mortality and recurrent CV events will be analyzed by LWYY model including treatment and baseline NT-proBNP as covariate. For subgroup analysis in the overall population, the model will also be stratified by baseline tafamidis use.

- Change from baseline in 6-MWT and KCCQ-OS:

Change from baseline in 6-MWT and KCCQ-OS will be analyzed by MMRM model with baseline value as a covariate, and treatment, visit, treatment-by-visit interaction as fixed effects. For subgroup analyses in the overall population, the model will also include baseline tafamidis use as a fixed factor.

- CCI [REDACTED]

- Change from baseline in NYHA class:

The binary outcome (stable or improved vs. worsened in NYHA Class at Month 30) will be analyzed by a CMH method stratified by baseline NT-proBNP. For subgroup analysis in the overall population, the model will also be stratified by baseline tafamidis use.

- Recurrent CV events:

The frequency of CV events will be analyzed by Poisson regression including treatment and baseline NT-proBNP as covariates. For subgroup analysis in the overall population, the model will also include baseline tafamidis use as a covariate.

Forest plots will be generated to illustrate the estimated treatment effect along with 95% CI within each subgroup.

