  mnar model (chg30m / modelobs=(treatment='placebo'));
  var baseline_variables base chg6m chg12m chg18m chg24m;
run;
```

For imputation using the retrieved dropouts (Pattern 3a and 4a), the multiple imputation approach described in [Wang 2022] is adopted.

Combining Results

Missing values will be imputed 100 times to generate 100 complete datasets using the procedures described above (via MI, CR or other methods described above). An analysis of covariance (ANCOVA) model will be fit to each imputed dataset for the change from baseline in 6-MWT/KCCQ-OS at Month 30. The ANCOVA model will include baseline 6-MWT/KCCQ-OS as a covariate and treatment arm, baseline tafamidis use, treatment by baseline tafamidis use interaction, ATTR disease type, and age group as factors. For the vutrisiran monotherapy subgroup analysis, baseline tafamidis use, and treatment by baseline tafamidis use interaction will be removed from the model. The LS mean and SE estimated from the ANCOVA model fit to each imputed dataset will be combined by applying Rubin's rules,[Rubin 1996; Rubin 1987] using SAS PROC MIANALYZE to produce inferential results including the treatment difference in LS means, 95% CI for the treatment difference, and the p-value.

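### Two pre-dose 6-minute walks are scheduled, but the visible 6-MWT models adjust for only one; adding the Screening walk as a covariate would give a small gain in precision

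*SAP*

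**What the plan says.** Protocol Table 1 marks the 6-MWT at both Screening and Day 1, and Protocol 6.2.3 confirms: "The 6-MWT will be performed at each of the timepoints specified in the Schedule of Assessments". The same section gives the purpose of the first walk: "At Screening, the 6-MWT will be administered for study eligibility purposes". Inclusion criterion 7 sets a minimum of 150 "meters on the 6-MWT at Screening", so every eligible patient should have a Screening distance. The Screening Period in Protocol 3.1 is "Up to 45 days during which patients will undergo screening assessments to determine eligibility", which bounds the gap between the two walks.

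For efficacy parameters, SAP 4.3 says that "baseline will be defined as the last non-missing value available on or before the date of the first dose of study drug", unless otherwise specified. It makes one exception for this test: "if a patient walked for ≤ 4 minutes at Day 1 visit, the screening visit will be used as baseline". Either way, one walk per patient enters as baseline. For pharmacodynamic parameters, the same section averages all pre-dose records.

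Three 6-MWT models can be read:
- The imputation model in SAP 9.4 has a single baseline term.
- The analysis that follows it: "The ANCOVA model will include baseline 6-MWT/KCCQ-OS as a covariate".
- The subgroup analysis in SAP 5.7.4: "will be analyzed by MMRM model with baseline value as a covariate".

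The primary MMRM (SAP 5.7.2.1.2) is redacted. SAP 4.6 places 6-MWT first among the secondary families in the alpha-controlled sequence.

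**The concern.** One walk is an imperfect measure of a patient's walking capacity. Its measurement error weakens the baseline adjustment, and the variance left unexplained stays in the Month 30 comparison. A second measurement of the same quantity, taken before treatment, is already being collected. In the visible models it is used only as a fallback, never alongside Day 1, and no visible text explains why.

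The stake is precision. 6-MWT gates the later secondary families: if neither 6-MWT hypothesis is rejected, testing stops before KCCQ-OS, all-cause mortality and NYHA class. If only one primary endpoint succeeds, 6-MWT is tested at 0.001.

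**Working it through.** **Plan's own figures.** The visible text gives no 6-MWT effect size, SD, power or correlation, so there is no sample-size figure to reproduce. The testing thresholds in SAP 4.6 do reproduce. With truncation fraction 0.96 and alpha 0.05, the larger-p bound is (0.96 + 0.04/2) × 0.05 = 0.049, the smaller-p bound is 0.05/2 = 0.025, and the alpha passed on is 0.05 − 0.049 = 0.001.

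**Inputs.**
- N = 600, allocated 1:1 (SAP 2.6, 2.4).
- About 40% on tafamidis at baseline (Protocol 10.4.1), so the monotherapy subgroup is about 600 × 0.6 = 360.
- Assumed, not in the documents: r, the correlation of one baseline walk with Month 30, 0.5-0.7; and ICC, the correlation between the two walks, 0.85-0.95.

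**Formula without deaths.** Adjusting for one walk leaves a fraction 1 − r² of the Month 30 variance. With two equally reliable walks the best linear combination is their mean, whose squared correlation with Month 30 is 2r²/(1 + ICC). The residual variance is therefore multiplied by

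VR = (1 − 2r²/(1 + ICC)) / (1 − r²).

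This is the share that remains; the fall is 1 − VR. Using change from Day 1 as the outcome makes no difference, because Day 1 is itself a covariate. The equivalent number of patients is 600 × (1/VR − 1).

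| r | ICC | VR | Fall | Patients of 600 |
|---|---|---|---|---|
| 0.5 | 0.95 | 0.7436/0.75 = 0.9915 | 0.9% | 5 |
| 0.6 | 0.90 | 0.6211/0.64 = 0.970 | 3.0% | 18 |
| 0.7 | 0.85 | 0.4703/0.51 = 0.922 | 7.8% | 51 |

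**With deaths.** The pattern mixture model draws the change for patients who died from the worst 10% of observed changes in the same group (SAP 9.4). Those values depend little on baseline capacity, so the gain shrinks. Simulating this rule with 10-20% deaths over the same range of r and ICC gives a fall of about 0.4-5%. At r = 0.6 and ICC = 0.90 it is 1.9% with 10% deaths and 1.3% with 20%:
- Of 600: 600 × (1/0.981 − 1) = 12 and 600 × (1/0.987 − 1) = 8 patients.
- Of 360: 360 × (1/0.981 − 1) = 7 and 360 × (1/0.987 − 1) = 5 patients.
- A test with 80% power at 0.049 rises to Φ(2.810/√0.981 − 1.969) = 80.8% or Φ(2.810/√0.987 − 1.969) = 80.5%.

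These figures move by up to roughly one percentage point depending on how strongly death is tied to walking capacity.

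**Bias check.** A separate simulation (600 patients, 1,500 replicates, true effect 15 m) added the 150 m entry threshold, a 10 m learning effect between walks and, in half the scenarios, deaths at about 20%. Adding Screening changed the mean estimated effect by no more than 0.12 m. Its variance ratios, 0.92-0.99, are not used for size because some scenarios lie above the assumed range of r. For example, ICC 0.95 with a 60 m drift SD implies r = 0.95 × 100/√(10,000 + 3,600) = 0.81.

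**The case against.** **The alpha-controlled model cannot be seen.** This stands. SAP 4.3 fixes what baseline means; it does not limit which other covariates the redacted MMRM may carry. A reader might infer that the primary 6-MWT analysis ignores Screening. The documents do not show that, and the visible models are sensitivity and subgroup analyses.

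**Taking the last pre-dose value is conventional and sensible.** This also stands. Day 1 is the walk nearest to dosing. Screening is an eligibility walk, up to 45 days earlier and truncated at 150 m, with possible learning. So it would be wrong to say that the rule has no merit. These features argue for keeping Day 1 as the reference for change; they do not argue against using Screening as a covariate.

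**A second, highly correlated term may strain the imputation.** This stands in part. SAP 9.4 imputes by treatment and tafamidis group and allows imputation from as few as 10 retrieved dropouts. In the final ANCOVA or MMRM, collinearity between the two baseline terms does not remove the gain in the treatment contrast.

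**Some patients may have only one usable walk.** SAP 4 admits only vendor-confirmed tests. Protocol 6.2.3 also says not to repeat a walk within 45 days, but in context that covers unscheduled, drop-in and discontinuation visits. Table 1 and SAP 4.3 both presuppose a Day 1 walk.

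**The 4-minute rule.** A reader might infer that replacing a short Day 1 walk with Screening records an existing limitation as later decline. The documents do not establish this. They do not say whether the vendor would confirm such a walk as valid, or whether it reflects lasting limitation or an interrupted test. The rule uses pre-treatment data identically in both arms, and no bias or size has been shown.

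**Conclusion.** The point holds as a modest efficiency improvement. Two pre-dose walks are planned, one is kept as baseline, and the visible models adjust for that one alone. Adding the other does not bias the randomised contrast. The fall in variance is 1-8% without deaths and about 0.4-5% with 10-20% deaths scored from the worst 10%. The central 1-2% is worth about 8-12 of 600 patients, or less than one point of power at 80%.

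The size rests on correlations and a death rate that the documents do not give, and on the death rule visible in SAP 9.4; the rule for the primary analysis is redacted. A reader might take the upper figure of about 50 patients as the expected gain, but that applies only with no deaths, the highest r and the lowest ICC. Nothing here is an error or a source of bias, and the 4-minute substitution rule can stay as it is.

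**What to change.** Keep change from the SAP 4.3 baseline as the outcome. Add Screening 6-MWT distance as a second continuous covariate in the 6-MWT ANCOVA (SAP 9.4) and the subgroup MMRM (SAP 5.7.4), and in the primary MMRM (SAP 5.7.2.1.2) if it is not already there. Add it to the pattern mixture imputation only where group sizes allow. State what value is used when the Screening walk was not confirmed as valid. Fix all of this before unblinding.

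The cost is one model degree of freedom in the final models and a short SAP addition. No new data are needed.

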4.4. Randomization Stratification Factors

Stratification factors are recorded in both the IRT and the clinical database. In statistical analyses which adjust randomization stratification factors in the model, the stratum assignment will reflect the values as recorded in the clinical database. In the presence of stratification errors, the stratification used in analysis may not match that in the IRT. A comparison of the number and percentage of patients in each randomization stratification factor in IRT versus the clinical database will be summarized by randomized treatment arm and overall, for all randomized patients. Data recorded in IRT and clinical database will be listed as well.

